7.4.3. CCI [REDACTED]

[REDACTED]

- | [REDACTED]
- | [REDACTED]
 - | [REDACTED]
 - | [REDACTED]
- | [REDACTED]

[REDACTED]

[REDACTED]

[REDACTED]

[REDACTED]

7.4.4. CCI [REDACTED]

[REDACTED]

- | [REDACTED]
 - | [REDACTED]
 - | [REDACTED]

Protocol 331-12-283

- CCI [REDACTED]

[REDACTED]

CCI [REDACTED]

7.5. Analysis of Demographic and Baseline Characteristics

Demographic characteristics and disease severity at baseline will be summarized by descriptive statistics, eg, proportion, mean, median, SD, and minimum and maximum values.

7.6. Safety Analysis

Standard safety variables to be analyzed include AEs, clinical laboratory tests, vital signs, ECGs, body weight, waist circumference and physical examination. In addition, data from the following safety scales will be evaluated: MMSE score, CCI [REDACTED]

[REDACTED] Safety analysis will be conducted based on the Safety Sample defined in [Section 7.2](#). In general, baseline of a safety variable is defined as the last observation of the variable before taking the first dose of IMP, unless specified otherwise. Prospectively defined criteria will be used to identify potentially clinically relevant abnormal values for clinical laboratory tests, vital signs, ECGs, and body weight. Details of safety analysis will be provided in the SAP.

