2.1. Trial Rationale

Behavioral symptoms, such as agitation, are core features in subjects with Alzheimer's disease and related dementias and develop in the majority of dementia subjects. The presence of agitation in subjects with Alzheimer's disease places a significant burden not only on subjects and their caregivers but also on the healthcare system.

Based on the data available from atypical antipsychotics in the treatment of agitation or aggression in Alzheimer's disease, brexpiprazole is an appropriate candidate to evaluate the benefit-risk ratio of this class of drugs in this subject population in today's clinical setting. In addition to potential treatment effects, the receptor binding profile of brexpiprazole may confer additional benefits in terms of the safety profile, particularly with respect to hyperprolactinemia, sleep quality, and weight gain.

In light of the Food and Drug Administration (FDA) boxed warning of increased mortality with the use of antipsychotics in elderly subjects with dementia-related psychosis and similar caution advised by other regulatory authorities, the clinical trial will be conducted in an environment that allows for close safety monitoring, in subjects who are living in either an institutionalized setting or in a non-institutionalized setting where the subject is not living alone and has a caregiver who can spend a minimum of 2 hours per day for 4 days per week with the subject in order to assess changes in the subject's condition. Furthermore, a slow titration schedule will be implemented with brexpiprazole being titrated to the highest assigned dose (2 mg/day) over a 4-week period. CCI [REDACTED]

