3.7. Trial Procedures

The time from enrollment of the first subject to the last subject’s last trial visit will be approximately 4.5 years, of which approximately 4 years are allotted for recruitment of subjects. Individual participation for subjects who complete the trial will range from 16 to 22 weeks, consisting of a 2- to 42-day screening period, a 12-week double-blind treatment period, and a 30-day follow-up period. All subjects will be followed up at a clinic visit or via telephone contact 30 (+ 2) days after the last dose of the IMP. [REDACTED]

[REDACTED]

CCI [REDACTED]

All trial visits will take place as a clinic visit at either the investigator’s site or residential facility, if applicable. All attempts should be made to maintain the subjects’ normal routine with regard to physician appointments. Individual circumstances that fall outside this general convention should be discussed with the medical monitor in order to determine appropriateness to proceed. Trial assessment time points are summarized in [Table 3.7-1](#).

Protocol 331-12-283

Table 3.7-1 Schedule of Assessments											
Assessment	Visit										
	Screening^a	Baseline (Day 0)	Day 3	Wk 2	Wk 4	Wk 6	Wk 8	Wk 10	Wk 12/ ET^b	FU^c	[REDACTED]
ENTRANCE/HISTORY											
Informed consent ^e	X										
Inclusion/exclusion criteria ^f	X	X									
Demography	X										
Medical history	X										
Psychiatric history	X										
Neurological history ^g	X										
Prior medication washout ^h	X										
NINCDS-ADRDA	X										
Hachinski Ischemic Scale (Rosen Modification) ^g	X										
HBsAg and anti-HCV	X										
[REDACTED]	█										
EFFICACY											
CMAI	X	X		X	X	X	X	X	X		
CGI-S ^j	X	X		X	X	X	X	X	X		
[REDACTED]				█	█	█	█	█	█		
[REDACTED]				█	█	█	█	█	█		
NPI-NH (for institutionalized subjects) or NPI/NPI-NH (for non-institutionalized subjects)	X	X		X	X	X	X	X	X		

Protocol 331-12-283

Table 3.7-1 Schedule of Assessments											
Assessment	Visit										
	Screening ^a	Baseline (Day 0)	Day 3	Wk 2	Wk 4	Wk 6	Wk 8	Wk 10	Wk 12/ ET ^b	FU ^c	█ ^d
OTHER											
CCI █		█								█	
█											
█											
SAFETY											
Physical examination ^k	X								X		
Neurological examination ^l	X								X		
Vital signs ^m	X	X	X	X	X	X	X	X	X		
Clinical laboratory tests (hematology, serum chemistry, urinalysis) ⁿ	X	X ^o			X ^p		X ^p		X		
Prolactin (blinded) ⁿ	X								X		
TSH with reflex to free T ₄ if abnormal ⁿ	X								X		
HbA _{1c} ⁿ	X								X		
PT, aPTT, and INR ⁿ	X								X		

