- ^b If a subject discontinues prematurely before Week 12, every effort should be made to complete the Week 12/ET evaluations prior to administering additional medications for the treatment of agitation or other prohibited medications.
- ^c All subjects, whether they complete the trial or are withdrawn prematurely for any reason, will be followed up for a safety evaluation 30 (+ 2) days after the last dose of IMP during a clinic visit at either the investigator's site or residential facility, if applicable. If a clinic visit is not possible, the subject should be assessed by telephone contact with the subject and a caregiver. Subjects who complete both the 12-week double-blind treatment period and the 30-day safety follow-up visit are eligible to enroll into Trial 331-13-211, which is a 2-month, observational, rollover trial to evaluate the safety of subjects with agitation associated with Alzheimer's disease who previously participated in Trial 331-12-283. For those subjects who plan to enroll into Trial 331-13-211, the 30-day safety follow-up visit for Trial 331-12-283 will occur as a clinic visit at either the investigator's site or residential facility, if applicable.
- ^d CCI
- ^e The investigator must assess the capacity of the subject to provide informed consent during the screening period and throughout the course of the trial. Once this determination is made by the investigator, the options for obtaining informed consent from and/or on behalf of the subject must be followed as provided in [Section 3.4.1](#).
- ^f The investigator is responsible for ensuring that subjects are eligible for enrollment into the trial and for assessing subject safety throughout the trial. CCI
- ^g The neurological history and Hachinski Ischemic Scale (Rosen Modification) will be completed to assess eligibility for the trial by the same physician who performs the neurological examination (refer to [Section 3.7.4.3.2](#)). The neurological history will include an MRI/CT scan as described in [Section 3.7.3.7](#) and as scheduled in the ADDITIONAL ENTRANCE/HISTORY.
- ^h Washout of prohibited medications begins after signing the ICF and must comply with the required washout periods (refer to [Section 4.1](#)).
- ⁱ CCI
- ^j CCI CGI-S, CCI are based on agitation.
- ^k Physical examination includes measurement of height and waist circumference at screening and waist circumference at Week 12/ET.

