- A detailed neurological examination, which will consist of an evaluation of the subject's mental status, cranial nerves, motor system (eg, motor strength, muscle tone, reflexes), cerebellar system (eg, coordination), gait and station, and sensory system, will be performed by a physician.
- Vital sign measurements (body weight, body temperature, blood pressure, and heart rate) will be recorded. Blood pressure and heart rate are to be measured in the following order: supine, sitting, and standing. Blood pressure and heart rate measurements in the supine position should be taken after the subject has been lying for at least 5 minutes. The sitting and standing measurements should be taken within 1 to 3 minutes of changing positions. See [Section 3.4.3](#) for exclusions based on outcome of screening vital sign measurements. Vital signs are to be completed before any blood is drawn.
- A standard 12-lead ECG will be performed after the subject has been supine and at rest for at least 5 minutes. Subjects with screening QTcF ≥ 450 msec (males) or ≥ 470 msec (females) will be excluded from the trial, unless due to ventricular pacing (see [Section 3.7.4.4](#)). Abnormal results for ECGs should be repeated once at screening with 3 consecutive ECG recordings to ensure reproducibility of the abnormality before excluding a subject. The ECG is to be completed before any blood is drawn.
- Blood samples will be drawn for the presence of hepatitis B surface antigen (HBsAg) and antibodies to hepatitis C (anti-HCV). Subjects with a positive result for any of these tests will be excluded from the trial. Vital sign and ECG assessments should be completed before any blood samples are collected.
- Blood samples will be collected for clinical laboratory tests (hematology, including PT, aPTT, and INR, and serum chemistry, including prolactin [blinded], HbA_{1c}, ACTH, cortisol, and TSH with reflex to free T₄ if the result for TSH is abnormal) and should be obtained after a minimum 8-hour fast, if possible. See [Section 3.7.4.2](#) for exclusions based on outcome of screening clinical laboratory tests. Vital signs and ECG assessments should be completed before any blood samples are collected.
- Samples will be obtained for blood alcohol testing. Subjects with a positive blood alcohol test at screening may be retested or rescreened once for participation in the trial with consent of the medical monitor.

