3.7.1.2. Baseline (Day 0)

If the subject is found to be eligible for the trial during the screening period, the following procedures will be performed at the baseline visit:

- CCI [REDACTED]
- Inclusion and exclusion criteria will be verified.
- The investigator must assess the capacity of the subject to provide informed consent throughout the course of the trial. Once this determination is made by the investigator, the options for obtaining informed consent from and/or on behalf of the subject must be followed as provided in [Section 3.4.1](#).
- A qualified and certified rater will administer the CMAI and NPI-NH (for institutionalized subjects) or NPI/NPI-NH (for non-institutionalized subjects) to the identified caregiver.
- An adequately trained and experienced clinician will administer the CGI-S.
- CCI [REDACTED]

Protocol 331-12-283

- CCI [REDACTED]
- [REDACTED]
- An adequately trained and experienced clinician will administer the MMSE.
- CCI [REDACTED]
- [REDACTED]
- Vital sign measurements (body weight, body temperature, blood pressure, and heart rate) will be recorded. Blood pressure and heart rate are to be measured in the following order: supine, sitting, and standing. Blood pressure and heart rate measurements in the supine position should be taken after the subject has been lying for at least 5 minutes. The sitting and standing measurements should be taken within 1 to 3 minutes of changing positions. Vital signs are to be completed before any blood is drawn.
- Blood samples will be collected for clinical laboratory tests (hematology and serum chemistry) and should be obtained after a minimum 8-hour fast, if possible. Urine will be collected for urinalysis. If a fasting blood sample was obtained at the screening visit and less than 14 days have elapsed since the screening visit, clinical laboratory tests (hematology, serum chemistry, and urinalysis) do not need to be repeated at the baseline visit. Vital signs and ECG assessments should be completed before any blood samples are collected.
- A standard 12-lead ECG will be performed after the subject has been supine and at rest for at least 5 minutes. The ECG is to be completed before any blood is drawn.

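### The prolactin baseline is a screening sample that may precede antipsychotic washout, so within-arm change from baseline mixes a washout effect with the drug effect

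*Protocol*

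**What the plan says.** **When prolactin is drawn.** In the Schedule of Assessments (Table 3.7-1) the row "Prolactin (blinded") is marked at Screening and Week 12/ET only. The visit sections agree. Section 3.7.1.1 includes it in the screening draw ("hematology, including PT, aPTT, and INR, and serum chemistry, including prolactin [blinded"]), and Section 3.7.1.4 names it again at Week 12/ET. Section 3.7.1.2 does not name it at Day 0: "Blood samples will be collected for clinical laboratory tests (hematology and serum chemistry) and should be obtained after a minimum 8-hour fast, if possible". That Day 0 draw can be left out: "If a fasting blood sample was obtained at the screening visit and less than 14 days have elapsed since the screening visit", the routine laboratory tests need not be repeated.

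**What counts as baseline.** Section 7.6 gives the general rule that "baseline of a safety variable is defined as the last observation of the variable before taking the first dose of IMP", unless specified otherwise. Sections 3.5.6 and 7.6.2 plan summaries of change from baseline for prolactin.

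**When prior drugs are stopped.** Footnote h of Table 3.7-1 states: "Washout of prohibited medications begins after signing the ICF and must comply with the required washout periods". Table 4.1-1 gives 7 days for antipsychotics in general, bars clozapine for 30 days before randomization, and sets 1.5 dosing intervals for depot products. Exclusion criterion 4 removes only subjects with an insufficient response to two or more antipsychotics, so other prior users can enter.

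**Why prolactin is of interest.** Section 2.1 says the receptor profile "may confer additional benefits in terms of the safety profile, particularly with respect to hyperprolactinemia, sleep quality, and weight gain".

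**The concern.** A change from baseline describes the effect of study treatment only if the baseline reflects the subject's state just before treatment. Here the single scheduled pre-dose sample may be taken while the subject is still on the drug to be washed out, and up to 42 days before Day 0 (longer if screening is extended). If that drug raises prolactin, stopping it lowers the Week 12 value whatever the study treatment does.

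This bears on how the active arms are read. Section 1 contrasts brexpiprazole with risperidone on prolactin, and also notes that risperidone is indicated for persistent aggression in Alzheimer's dementia in some EU countries, so prior use in a worldwide trial is plausible. A mean fall in an active arm could be taken as a favourable drug effect when it is washout, or a modest drug-related rise could be masked.

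The statistical analysis plan can choose how to present change, but it cannot create a post-washout sample that was never scheduled. The gap lies in the collection schedule.

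**Working it through.** The protocol states no figure on this point, so there is none to reproduce. The check sets the passages side by side and then uses a simple decomposition.

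**Step 1: which sample is the baseline.** Scheduled pre-dose prolactin samples: Screening only (Table 3.7-1; Sections 3.7.1.1 and 3.7.1.2). Applying the last-pre-dose rule of Section 7.6, the baseline is the screening value unless an unscheduled sample exists.

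**Step 2: can it be on-drug.** Screening procedures start between Day -42 and Day -2. Washout starts after consent, within the same period. No text orders the draw after washout. A draw at the first screening visit therefore precedes trial-driven washout; a draw at a later screening visit may follow it, since Section 3.7.1.1 allows more than one visit.

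**Step 3: what this does to the summaries.** Let p be the share on a prolactin-raising drug at the draw, W their mean fall after stopping, and D the true effect of study treatment. Neither p nor W is in the protocol.

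- Expected within-arm change = D - p x W, with D = 0 for placebo.
- Expected active-minus-placebo difference = (D - pW) - (0 - pW) = D. The washout term cancels because the sample precedes randomization.

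For assumed p of 0.1 to 0.5, the within-arm shift is -0.1W to -0.5W.

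**Step 4: illustration.** Assumed inputs: D = +2 units, residual SD of change 8, W of 10 or 30 units, 140 per arm (420/3), 4,000 simulated trials. The expected SD of the difference is sqrt(2 x (8² + W²p(1-p))/140), which is sqrt(128/140) = 0.96 with no washout effect.

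| p | W | Active-arm change, 2 - pW | Simulated | Simulated difference from placebo | Simulated SD of difference |
|---|---|---|---|---|---|
| 0.1 | 10 | +1 | +1.0 | 2.03 | 1.01 |
| 0.1 | 30 | -1 | -0.97 | 2.03 | 1.45 |
| 0.3 | 10 | -1 | -1.0 | 2.00 | 1.13 |
| 0.3 | 30 | -7 | -6.95 | 2.08 | 1.91 |
| 0.5 | 10 | -3 | -3.0 | 1.97 | 1.12 |
| 0.5 | 30 | -13 | -13.0 | 2.01 | 2.03 |

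Under these assumptions a true rise of 2 units appears as a fall within the arm in five of six settings. The difference from placebo stays near 2 in all six, but its SD rises from about 1 to about 2.

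**Step 5: the 14-day waiver.** If someone read prolactin as part of the Day 0 chemistry panel, that draw can still be skipped when a fasting screening sample is under 14 days old. A 7-day washout fits inside 14 days, so an on-drug baseline remains possible on that reading too.

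**The case against.** The strongest reply is that the secondary objective (Section 2.3) is safety compared with placebo, and that comparison is not biased. Any washout shift is equal in expectation in the placebo arm, so it can hide a rise only if an active arm is read without its control. This stands. A reader might infer that the prolactin comparison with placebo is invalid; the documents do not support that.

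Two further points stand. Section 3.5.6 also plans the incidence of potentially clinically relevant values, and Appendix 3 sets the prolactin criterion as above the upper limit of normal with no change-from-baseline condition, so baseline timing does not affect it. And the protocol supplies neither p nor W, so any shift stated in concentration units would only be the product of guesses.

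A reader might also see a contradiction, because Table 3.7.4.2-1 lists prolactin under serum chemistry and serum chemistry is drawn at Day 0. That goes too far. The table groups analytes and gives no visit for prolactin; Table 3.7-1 has a separate prolactin row, and the visit text follows it. Panel labels are used loosely elsewhere: Section 3.7.1.1 lists HbA1c, ACTH, cortisol and TSH with serum chemistry, while Table 3.7.4.2-1 puts them under additional tests. It is at most an ambiguity of labels.

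Section 7.6 speaks in general terms and leaves detail to the statistical analysis plan. That plan could show change by prior antipsychotic use, which would help, but it would leave the affected subjects without a usable baseline.

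**Conclusion.** The point holds for within-arm change. As scheduled, the prolactin baseline is a screening value that may precede antipsychotic washout, and each arm's mean change then contains -p x W in addition to any drug effect. The size is unknown because p and W are not in the protocol; the range of -0.1W to -0.5W rests on an assumed p of 0.1 to 0.5. Only subjects on a prolactin-raising drug at the draw contribute.

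The difference from placebo remains unbiased (missing follow-up aside) and loses precision. The incidence above the upper limit of normal is untouched by baseline timing. This is a cheap improvement to a descriptive safety summary, not a flaw in the trial's safety comparison.

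**What to change.** 1. Add a blinded prolactin assay at Baseline (Day 0) in Table 3.7-1 and Section 3.7.1.2, and use it as the prolactin baseline. Include subjects whose Day 0 chemistry is waived under the 14-day rule, or at least those among them who washed out an antipsychotic.
2. State in Table 3.7.4.2-1 that prolactin is drawn only at the visits marked in Table 3.7-1. Aligning Table 3.7-1 to the chemistry panel instead would imply prolactin at Weeks 4 and 8 as well, since serum chemistry is drawn then.
3. If no sample can be added, interpret only placebo-adjusted change, shown by antipsychotic use at the screening draw. Medications taken within 30 days of screening are already recorded.

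Cost: one extra assay per subject where Day 0 blood is drawn anyway, and a short extra blood draw for those otherwise exempt, which is a real burden in agitated patients with dementia; the protocol does not say how many would be exempt. The Day 0 sample removes most of the washout component and sharpens the contrast with placebo, but carry-over from depot drugs may remain.

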7.6.1. Adverse Events

All AEs will be coded by system organ class and Medical Dictionary for Regulatory Activities (MedDRA) preferred term. The incidence of the following events will be summarized by treatment group:

- 1) TEAEs by severity
- 2) TEAEs potentially causally related to the IMP

Protocol 331-12-283

- 3) TEAEs with an outcome of death
- 4) Serious TEAEs
- 5) Discontinuations due to TEAEs

7.6.2. Clinical Laboratory Data

Summary statistics for changes from baseline in the routine clinical laboratory measurements, prolactin concentrations, coagulation parameters (PT, aPTT, and INR), HbA_{1c}, cortisol, ACTH, and TSH will be provided. In addition, the incidence of potentially clinically relevant values identified using prospectively defined criteria for laboratory tests will be summarized.

7.6.3. Physical and Neurological Examination and Vital Signs Data

Physical and neurological examination findings will be listed by subject. Potentially clinically relevant results in vital signs and body weight will also be summarized. Summary statistics for change from baseline in vital signs, body weight, and waist circumference will be provided.

7.6.4. ECG Data

Mean change from baseline will be summarized by treatment group and by visit. Incidence of clinically relevant changes will be calculated for ECG parameters and summarized by treatment group and by visit.

For the analysis of QT and QTc data from three consecutive complexes (representing three consecutive heart beats) will be measured to determine average values. The following QT corrections will be used:

- 1) QTcB is the length of the QT interval corrected for heart rate by the Bazett formula: $QTcB = QT / (RR)^{0.5}$, and
- 2) QTcF is the length of the QT interval corrected for heart rate by the Fridericia formula: $QTcF = QT / (RR)^{0.33}$
- 3) QTcN is the length of the QT interval corrected for heart rate by the FDA Neuropharm Division formula: $QTcN = QT / (RR)^{0.37}$

Results will be summarized by visit.

Protocol 331-12-283

7.6.5. [CCI] [REDACTED]

[REDACTED]

7.7. [CCI] [REDACTED]

[REDACTED]

8. Management of Investigational Medicinal Product

8.1. Packaging and Labeling

Trial medication will be provided to the investigator(s) by the sponsor or designated agent. The IMP will be supplied as active brexpiprazole tablets or matching placebo tablets. The 0.25 mg/day dose will be supplied as a blister card containing sufficient tablets for 3 (+2) days; the 0.5 mg/day, 1 mg/day, and 2 mg/day doses will be supplied as weekly blister cards, each containing sufficient tablets for 7 (+ 2) days. When accessed by the site, the IVRS or IWRS will assign specific blister card number(s) to be dispensed to a subject.

Each blister card of brexpiprazole or matching placebo used in the trial will be given an identifying number and will be labeled to clearly disclose the blister card number, Site number (to be filled in by the site staff/investigator), Subject ID (to be filled in by the site staff/investigator), subject's initials or other unique identifier (to be filled in by the site staff/investigator), compound ID, protocol number, the sponsor's name and address, instructions for use, route of administration, and appropriate precautionary statements.

Protocol 331-12-283

Once a blister card has been assigned to a subject via the IVRS or IWRS, it cannot be dispensed to another subject.

